3 OBJECTIVES AND ENDPOINTS

OBJECTIVES	ENDPOINTS	JUSTIFICATION FOR ENDPOINTS
Primary		
	Performance/Effectiveness: DA Ratio of the Wave PRO system as compared to the predicate ECP device at the eighth minute of ECP compressions (out of 10 total compression minutes)	DA ratio was chosen as the primary endpoint of this study because it is a direct and objective measure of the hemodynamic effect of ECP. DA ratio is a unitless measure which is “calculated as the ratio of the peak diastolic amplitude divided by the peak systolic amplitude” ¹ . ECP causes diastolic amplitude to increase relative to systolic amplitude. DA ratio noninvasively characterizes the hemodynamic effect of ECP and is correlated to clinical effectiveness of the treatment, as described in the literature cited in this protocol. DA ratio can be measured by use of a second independent PPG sensor for the Wave PRO and by the onboard PPG sensor on the predicate ECP device. Due to these characteristics, DA ratio is an appropriate endpoint for assessing substantial equivalence of Wave to the predicate device.
Secondary		
	Safety: 
 ○ Occurrence of device-related Serious Adverse Events ○ Device-related Adverse Event rate 	Occurrence of device-related SAEs and AEs are appropriate endpoints for evaluation of safety because they are direct measures of the effect of the Wave PRO device on study participants. It is reasonable to consider only device-related AEs/SAEs and not all AEs/SAEs when evaluating the investigational device, as non-device-related AEs/SAEs will be irrelevant.

OBJECTIVES	ENDPOINTS	JUSTIFICATION FOR ENDPOINTS

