8.3 SAFETY AND OTHER ASSESSMENTS

Adverse Events/Serious Adverse Events (SAEs) will be recorded on the Adverse Event eCRF from the time the participant signs Informed Consent until study exit. The Investigator and any qualified designees are responsible for detecting, documenting, and recording events that meet the definition of an AE or SAE in the AE eCRF and remain responsible for following up all AEs.

The participant will be asked to complete surveys after each ECP device session and again one day after completion of the study procedures.

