8.4.3.2 RELATIONSHIP TO STUDY INTERVENTION

The Investigator, on the basis of his or her clinical judgment, should determine whether there is a reasonable possibility the study device or procedure caused or contributed to the event. Guidelines to assess relatedness of an AE are provided below:

- **Not related:** The adverse event is determined to be solely caused by the underlying disease, disorder or condition of the participant, or attributable solely to other extraneous causes (unrelated to the device, device malfunction, or the procedure).
- **Unlikely related:** The adverse event onset does not follow a sequence of time from procedure for which the event could be attributed to the administration or procedure, and/or can be attributable to the underlying disease, disorder or condition of the participant, or attributable to other extraneous causes.
- **Possibly related:** The adverse event has onset within a clinically relevant temporal relationship to exposure to the device or procedure and is more likely than not to be at least partially caused by or aggravated by the use of the device, device malfunction, or the procedure. It must also meet both of the following criteria: (1) follows a known or easily foreseen pattern of response to device use or procedure; and (2) is not fully attributable to the underlying disease, disorder or condition of the participant, or attributable to other extraneous causes. In addition, if the adverse effect is reversible upon reoperation or device exchange, and such a procedure is done, the effect disappears or lessens in severity within the expected time interval.
- **Probable or highly probable related:** The adverse event is clearly caused by the use of the device, device malfunction, or the procedure. It must meet all the following criteria: (1) has a clear temporal relationship between device exposure and onset of the event; (2) follows a known pattern of response to device use or procedure; and (3) is not reasonably attributable to the underlying disease, disorder or condition of the participant, or attributable to other extraneous causes. In addition, if the adverse effect is reversible upon reoperation or device exchange, and such a procedure is done, the effect disappears or lessens in severity within the expected time interval.

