9.3.2 SAFETY ENDPOINTS**Safety Endpoint 1:**

Occurrence of device-related Serious Adverse Events (SAEs) as reported on the case report forms.

Analysis cohort: Safety cohort.

Analysis methods:

The number of events, number of participants and proportion of participants experiencing any device-related SAE will be summarized by treatment arm. There are no hypothesis tests, but 95% CI for the proportion of participants with an event may be calculated.

Safety Endpoint 2:

Rate of device-related Adverse Events (AEs) as reported on the case report forms.

Analysis cohort: Safety cohort.

Analysis methods:

The number of events, number of participants and proportion of participants experiencing any device-related AE (including serious) will be summarized by treatment arm. There are no hypothesis tests, but 95% CI for the proportion of participants with an event may be calculated.

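### Section 9.3.2 tabulates only device-related AEs and SAEs; adding all-cause counts and a listing would be a minor, cheap improvement

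*Combined protocol and SAP*

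**What the plan says.** **Collection.** Section 8.4.1 defines an AE without regard to cause. Section 8.3 states that AEs and SAEs "will be recorded on the Adverse Event eCRF from the time the participant signs Informed Consent until study exit".

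**Analysis.** Section 9.3.2 specifies two safety summaries in the Safety cohort. For Safety Endpoint 1, the "proportion of participants experiencing any device-related SAE will be summarized by treatment arm". For Safety Endpoint 2, the "proportion of participants experiencing any device-related AE (including serious) will be summarized by treatment arm". Counts of events and of participants accompany each. There is no hypothesis test, and a confidence interval is optional.

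**Rationale.** Section 3 defends the restriction: "It is reasonable to consider only device-related AEs/SAEs and not all AEs/SAEs when evaluating the investigational device, as non-device-related AEs/SAEs will be irrelevant".

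**Causality.** Section 8.4.3.2 asks the Investigator to determine "whether there is a reasonable possibility the study device or procedure caused or contributed to the event", and then gives four categories as guidelines: *Not*, *Unlikely*, *Possibly*, and *Probable or highly probable* related. Neither that section nor 9.3.2 states which of them make an event device-related.

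**The concern.** The plan collects events of every cause and then commits to tabulating only those attributed to the device. The safety result therefore rests on individual causality calls. Section 6.6 says that participants and operators cannot be blinded to the device, and it describes no blinding for the Investigator who makes those calls.

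The event type of most interest is also one that can readily be attributed to something else. Section 5.1 requires a history of mild to moderate CAD in every participant, and section 2.3.1 lists a rise in cardiac adverse events among the rare effects of counterpulsation. If such an event is put down to background disease, both planned summaries could show zero although the event is on the AE eCRF. A reader of those summaries could neither see it nor judge the attribution.

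**Working it through.** The plan states no safety rate or safety sample size, so there is no figure to reproduce. The 44 paired participants (about 50 randomized, 44/0.88 = 50) serve the primary endpoint and play no part here. The check is to follow one event through the text: a cardiac event in a participant with CAD, with onset after a session.

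**Step 1. Is it recorded?** Yes. Sections 8.3 and 8.4.1 cover it whatever its cause.

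**Step 2. How is it classified under section 8.4.3.2?**

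- *Not related*: "The adverse event is determined to be solely caused by the underlying disease, disorder or condition of the participant", or solely by some other outside cause.
- *Unlikely related*: the timing does not fit, "and/or can be attributable to the underlying disease, disorder or condition of the participant, or attributable to other extraneous causes". Because of the and/or, a possible attribution to disease can be enough.
- *Possibly related*: the timing is clinically relevant and the event "is more likely than not to be at least partially caused by or aggravated by the use of the device". It must also follow a known or foreseeable pattern and not be fully explained by disease or other causes.
- *Probable or highly probable related*: clearly caused by the device or procedure.

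The opening test and the third category set different bars. The opening test asks for a reasonable possibility. *Possibly related* asks for better than even odds of at least partial causation. An event with a reasonable but less than even chance of device contribution, in someone with CAD, passes the opening test, misses *Possibly related* and fits *Unlikely related*.

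**Step 3. Does it enter section 9.3.2?** Rated *Not related*, it does not. Rated *Unlikely related*, it does not on the ordinary reading of the scale.

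**Step 4. Does it appear in any other planned output?**

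| Section | What it provides | All-cause AE count? |
|---|---|---|
| 9.1 | General default of descriptive summaries | Names no AE table |
| 9.3.1 | Separate summary of participants who cannot tolerate therapy | No |
| 9.3.3 | Completion of 10 minutes, per device | No |
| 9.3.5 | Subgroup summaries | Effectiveness endpoints only |
| 9.3.6 | Exploratory analyses | None planned |
| 7.2 | Withdrawal reason on the exit form | No |
| 8.4.5 | SAEs to the sponsor within 24 hours, UADE assessment | Case review only |
| 10.1.4 | Medical Monitor evaluates AEs | Case review only |
| 10.1.5 | Full source verification of AE documentation | Data quality only |

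The event is recorded and open to case-level review, but no planned table or listing has to show it.

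**The case against.** The strongest reply has four parts.

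- **Low stakes.** Exposure is two 10-minute sessions, follow-up is a call one to three days later, and safety carries no test. Unrelated events should be few. This stands, and it is why the point is minor.
- **A choice of endpoint, not a ban.** Section 3 justifies which events serve as endpoints, and section 9.1 could be read as covering everything on the AE eCRF. It is true that nothing prohibits an all-cause table. But section 9.1 does not mention AEs, and a general default cannot be relied on against a specific statement that the other events do not matter.
- **A narrow scenario.** A cardiac event during or soon after compression has the timing and foreseeable pattern that *Possibly related* requires, and *Not related* demands sole causation by something else. This also stands in part: several conditions must coincide before such an event drops out.
- **The cut-point is obvious.** Most readers would take *Possibly* and *Probable or highly probable* as related. That is fair, so the missing cut-point is mostly a matter of detail. Writing down that mapping alone would not settle it, because the better-than-even wording would still leave out events that meet the opening test.

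A reader might infer that cardiac events would go unreviewed or be hidden. The documents do not support that: sections 8.4.5, 10.1.4 and 10.1.5 provide for expedited SAE reporting, medical review and source verification. Nor do they show that the Investigator's causality calls would be biased. They only describe no blinding for them.

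**Conclusion.** The point holds as a minor reporting improvement. The two planned AE summaries depend wholly on attribution. The all-cause data are collected, and nothing in the plan commits to counting or listing them.

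The effect cannot be given a number. The only prior experience quoted is no adverse events in 150 healthy volunteers on predecessor technology and none in the seven-person pilot (section 1.1), which gives no usable rate for a population with CAD. Any interval would rest on invented event counts. The sample size, alpha and primary non-inferiority conclusion are unaffected.

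The conclusion assumes that section 9.3.2 is applied as written and that section 9.1 is not taken as a commitment to an all-cause table. A reader might go further and treat the safety endpoints as uninterpretable because no cut-point is stated. The ordinary reading of the four categories is workable, so that does not follow.

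**What to change.** In section 9.3.2:

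1. Add, for the Safety cohort, the event count and the count and percentage of participants with any AE and with any SAE regardless of cause, overall and by section 8.4.3.2 category.
2. Add a listing of all AEs with event type, relatedness category, onset date and time where recorded, and the device session or sessions that preceded onset.
3. Keep the device-related summaries as the endpoints. Count as device-related every event that meets the reasonable-possibility test of section 8.4.3.2, and reword *Possibly related* so that it matches. That test rates device and procedure together, so label the table accordingly.

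In section 3, remove the sentence that dismisses events not related to the device.

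The cost is some wording, one table and one listing from events already captured on the AE eCRF. No passage shows that the form holds onset time relative to a session, so the listing should use what is recorded. The AE figures will look slightly less favourable because unrelated events appear as well. Both sessions fall on the same day with a 20-minute washout, so an event after the second session cannot be cleanly assigned to one device and should be reported as following both.

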4 STUDY DESIGN

4.1 OVERALL DESIGN

Potential study participants will be recruited per standard practices of the clinical research facility (may include advertising/publicity). Participants will be consented prior to any study related assessments/procedures. Only eligible participants that meet the required criteria (inclusion/exclusion) will be enrolled in the study and subsequently randomized to the ECP devices. Overall study design is shown in **Figure 1**. For the Wave PRO, PPG waveforms will be collected with an independent data acquisition system, BIOPAC (Goleta, CA). The predicate device has onboard data capture and analysis functionalities.

Steps for the Clinical Site for each randomized participant (see Section 6):

- For the Wave PRO: setup (recorded time), rest period (supine, recorded blood pressure and heart rate), pre-compression baseline PPG (recorded on BIOPAC), compression period (automated inflation/deflation tuning, PPG recorded on BIOPAC), post-compression PPG (recorded on BIOPAC), and end of session procedures (recorded blood pressure and heart rate, Wave PRO questionnaire administered).
- For the predicate ACS NCP-2: setup (recorded time, participant profile created), rest period (supine, recorded blood pressure and heart rate), compression period (manual inflation/deflation tuning required, PPG recorded on predicate device), and end of session procedures (recorded blood pressure and heart rate, predicate questionnaire administered).

There will be a 20-minute washout period between the two ECP device sessions, requiring the participant to walk around (no strenuous or high-intensity activities). An observation period will be required after the last test session. A final questionnaire will be conducted during the follow-up call the next day.

Signal Processing steps include (see Section 6):

- For the Wave PRO: average DA ratio will be measured using an R script that processes the BIOPAC waveform data at the 8th minute of compression (i.e., minute 7 to minute 8 of compressions). Average systolic amplitude of the last 10 waveforms of baseline before compressions and the average amplitude of the systolic amplitude of the first 10 waveforms during compressions will be recorded for systolic unloading calculations.
- For the predicate ACS NCP-2 device: average DA ratio in the 8th minute of compressions will be calculated using an R script that processes the waveforms collected by the ACS software. The predicate device only allows for analysis of 8-second time strips at a time. No systolic unloading calculation for the predicate device.

During Signal Processing, the evaluator will be blinded to the paired participant testing (i.e., blinded to the participant ID). The blinded evaluator will not be able to match a participant's test on the Wave PRO with that of the predicate device. However, given the nature of the data collected, the evaluator will not be blinded to which ECP device the data pertains to. The

blinded evaluator will record the DA ratio in the CRF for each tested ECP device. For the Wave PRO, the blinded evaluator will also record the average systolic amplitudes.

Statistical analysis steps include (see Section 9)

- An ANOVA model for crossover design will be performed and the pairwise difference between two treatments DA ratios (Wave PRO – predicate ECP) in the treatment least square mean and its 95% CI will be constructed. Non-inferiority margin will be set at -0.15.
- Descriptive analysis will be conducted for all secondary endpoints.

During Statistical analysis, the statistician will be provided the DA ratio values (per ECP device) matched to each participant ID.

[figure not shown]

Figure 1: Study design schematic, including steps at the Clinical Site, Signal Processing, and Statistics. ¹Washout period between the ECP devices for each randomized participant will include walking around, ²Duration of setup will be recorded, ³Average DA ratio in the 8th minute of compressions (BIOPAC data, R script analysis), ⁴Average DA ratio in the 8th minute of compressions (ACS NCP-2 data, R script analysis), ⁵Average systolic amplitude of the last 10 waveforms of baseline and the systolic amplitude of the first 10 waveforms during compressions, ⁶Compared to non-inferiority margin (see stats description).

4.2 JUSTIFICATION OF STUDY DESIGN

As the purpose of the study is to demonstrate substantial equivalence of hemodynamic effect of the Wave PRO ECP system to a predicate ECP device, the study is intended to test the two devices in head-to-head fashion.

This study is a randomized crossover study enrolling up to 50 participants in order to have 44 completing participants. Each participant will receive ECP compressions from the Wave PRO device and from the predicate (ACS NCP-2) ECP device, one at a time, and with the sequence of device use randomized to control bias. Pression has utilized accepted biostatistical study design principles to calculate the sample size of the clinical study to reach adequate power to prove substantial equivalence (non-inferiority) of the DA ratio achieved by the Wave PRO compared to the predicate ECP device.

The Diastolic Augmentation (DA) ratio, also referred to as Diastolic/Systolic (D/S) ratio and Effectiveness Ratio (ER), noninvasively characterizes the hemodynamic effect, and thus the clinical effectiveness, of ECP treatment. Predicate device Instructions for Use (IFU) and ECP literature direct medical professionals to utilize this metric to optimize the treatment: “The treatment aims to create an enhanced [DA ratio] during cardiac diastole” and “[DA] ratio [is] monitored using standard finger photoplethysmography [PPG]”⁹. Medical professionals delivering ECP treatment are further trained to recognize permutations of the PPG waveform that indicate whether a treatment is being effectively delivered or whether the treatment parameters require adjustment. The hemodynamic impact of these adjustments is measured solely by way of the PPG waveform.

While the predicate device has built-in functionality to capture PPG waveforms, the Wave PRO has no onboard PPG waveform capturing capability. Therefore, for the purposes of this study, a dedicated and independent data acquisition system, BIOPAC, will be used.

DA ratio will be calculated by a qualified blinded evaluator (blinded to participant ID and ECP session pairing). A computer containing the ACS software (provided by Pression) will be used to review the ACS NCP-2 data and capture screenshots of the data, enabling the R script (provided by Pression) to process the data and calculate DA ratio, in accordance with the IFU. For the Wave PRO, raw data obtained from the dedicated BIOPAC data acquisition system will be evaluated using a separate custom R-script code (which Pression will provide). In effect, the same DA ratio calculation of the eighth minute of compressions for both systems will be conducted.

Internal testing has demonstrated that diastolic augmentation can be observed almost immediately at the start of an ECP session. The initial response of the participant to the ECP device can be assessed after the first 5 minutes of compression, so the 10 minute compression time is appropriate.

Per the ACS NCP-2 IFU regarding compression pressures on the first day (to be set by the operator at the clinical site), pressures will be set to 3PSI, from a maximum of 6PSI. Pressures are typically set to however much patients are able to tolerate, and more pressure does not always equate to higher augmentation in the predicate ECP device.

4.3 END OF STUDY DEFINITION

There will be approximately 10 minute observational period at the conclusion of the second ECP device session. The participant will be provided a post-session questionnaire regarding their ECP experience after each ECP device test. Once the participant has received their +1-day follow-up phone call and questionnaire, they will be considered exited from the study.

5 STUDY POPULATION

5.1 INCLUSION CRITERIA

Each participant must meet all of the following Inclusion Criteria to be considered eligible for the study.

- Age 35 years or greater
- History of mild to moderate coronary artery disease (CAD), as evidenced by one or more of the following:
 - Angina pectoris
 - Canadian Cardiovascular Society (CCS) Angina classes I or II
 - Prior confirmation of CAD from invasive or noninvasive studies
 - Prior myocardial infarction (MI)
 - Prior coronary artery bypass graft (CABG) surgery
 - Prior cardiac stents
- Able to ambulate without assistance (no cane or walker)
- Able to lay down (approximately 5 degree angle) for the duration of the protocol required procedures
- Able and willing to give informed consent
- Able and willing to participate in the clinical study and complete all questionnaires provided

5.2 EXCLUSION CRITERIA

Participants must not meet any of the following Exclusion Criteria to be considered eligible for the study.

- Unstable angina within prior 3 months
- Canadian Cardiovascular Society (CCS) Class III or IV Angina
- Moderate to severe peripheral arterial disease (PAD)
 - ABI < 0.8
- Myocardial infarction in the past 3 months
- Coronary artery bypass grafting (CABG) in the past 3 months
- Any major surgery within the past 3 months
- Decompensated heart failure
- Cardiac catheterization or arterial femoral puncture in the past 2 weeks
- Presence of mechanical circulatory support (MCS) device
- Pacemaker or other implantable pulse generating device
- Valve disease, including aortic insufficiency
- Abdominal or thoracic aortic dissection or aortic/cerebral aneurysms requiring clinical intervention
- Severe pulmonary disease
- Bleeding diathesis
- Patients undergoing warfarin anti-coagulation therapy, or with PT-INR > 2.5, or who have routine INR or prothrombin time tests Active thrombophlebitis
- Uncontrolled hypertension (greater than 180/110 mmHg)
- Baseline heart rate > 120 beats per minute or < 40 beats per minute
- Arrhythmia and/or abnormal heart rhythm

- Major hand injuries or amputation that would interfere with finger PPG
- Unhealed wounds/fractures below the waist or lower limb amputation, major lower body musculoskeletal injuries
- Lower body vascular stents (arterial/venous)
- Currently undergoing ECP treatment
- Pregnancy
- Currently participating in any other clinical study of an investigational device or drug where treatment has not yet been completed
- Any medical condition that, in the opinion of the principal investigator (PI), would present undue risk to the participant

